# 4. ELIGIBILITY CRITERIA

#### 4.1 Inclusion Criteria

- Age  $\geq$ 18 years.
- Karnofsky Performance Status >70% (see Appendix II).
- Histologically confirmed adenocarcinoma of the pancreas or ampulla of Vater; at least the majority of the histopathologic specimen must be identified as adenocarcinoma as opposed to another histologic subtype. In patients with a diagnosis of recurrent disease (based on radiographic progression and/or rising CA19-9 levels) and a history of a biopsy-proven adenocarcinoma of the pancreas or the ampulla of Vater, repeat biopsy of the recurrence site is not required for participation of the trial.
- Pancreatic or periampullary tumors must be less than 8.0 cm in greatest axial dimension at the time of treatment planning.
- Patients who have been treated with any combination of surgical resection and neoadjuvant/adjuvant conventional chemoradiation therapy for resectable disease or conventional chemoradiation as definitive treatment for unresectable or borderline resectable disease are eligible for the study, provided that at least 180 days have elapsed since completing any previous radiation treatment. Patients who have been receiving continued chemotherapy following their initial radiation treatment are eligible regardless of when the most recent chemotherapy was received. Those patients who have received prior radiation therapy will constitute Cohort A and will receive SBRT as 5 Gy x 5.
- Patients who have not previously undergone radiation therapy can have a history of treatment with either chemotherapy (for unresectable/borderline resectable disease) or any combination of surgery and chemotherapy (for resectable disease). Patients with no history of prior radiation treatment will constitute Cohort B and will receive SBRT as 6.6 Gy x 5. Please note that patients must have received at least two cycles of chemotherapy (with selection of drugs at the discretion of the treating oncologist) before SBRT treatment on protocol.
- Acceptable organ and marrow function as defined below (taken no earlier than time of CT Simulation, within 3 weeks prior to radiotherapy):
  - Leukocytes >3,000/μL

- O Absolute neutrophil count >1,500μL
- $\circ$  Platelets > 100,000/ $\mu$ L
- o Total Bilirubin ≤1.5x institutional upper limit of normal
- AST(SGOT)/ALT(SGPT) <2.5x institutional upper limit of normal

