# 7. SBRT ADMINISTRATION AND RADIATION TREATMENT

# 7.1 Pre-Linac-based SBRT Tests, Procedures, and Planning

The following will be completed prior to Linac-based SBRT:

- Medical history and clinical examination.
- CBC with differential, chemistry panel, and CA19-9 measurement.
- Gold fiducial seed placement percutaneously, intraoperatively, or under endoscopic ultrasound guidance, which may be performed prior to enrollment.
- Pathologic confirmation of malignancy. (Core biopsies may be obtained during gold fiducial placement as needed; however, repeat biopsy is NOT required for study enrollment in patients who already have pathologically proved adenocarcinoma of the pancreas or periampullary region.)
- Pancreatic-protocol CT or CT of the chest/abdomen/pelvis
- Baseline FDG-PET/CT (dual phase) may be obtained for tumor staging and treatment planning purposes; however, patients who are unable to undergo PET CT scanning (e.g., due to insurance refusal of coverage) can still participate in the study.
- Signed informed consent document.
- Baseline collection of EORTC QLQ C-30/ PAN26 QOL.

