#### Footnotes:

- Within 45 days of commencing study treatment.
- Urine or serum pregnancy test must be negative in all premenopausal women who have not undergone surgical sterilization procedures.
- FDG PET scan optional at baseline and at all follow-up intervals.
- All follow-up visits subsequent to the 4-6 week visit may be completed at an outside hospital. However, all records and imaging (copies of images in addition to reports) must be reviewed at IU. Follow-up appointments have a 30-day tolerance window. QoL surveys may be returned by mail for patients who are completing follow-up visits at an outside clinic.
- A treatment evaluation will be done in lieu of history/physical exam at these visits.
-  Surgical oncology visit note is acceptable if patient has undergone surgical procedures and is limited to travel to clinic

Protocol Version Date: 07/02/2024 Page 18

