#### 10. CRITERIA FOR EVALUATION/REMOVAL FROM STUDY

# **10.1** Anti-Tumor Effect and Response Evaluations

Patients will be evaluated for anti-tumor effect by follow-up imaging (pancreas protocol CT and/or PET-CT imaging) as outlined above. All subsequent scans (post-treatment) will be compared to the same pretreatment CT or PET/CT that was performed for radiation treatment planning. Evaluation of pancreatic and periampullary tumor response will be based on standard radiographic criteria for the treated lesion and will be prospectively recorded in the study database. Radiographic response of the pancreatic or periampullary tumor by diagnostic CT scans will be defined according to RECIST criteria as described below:

- CR = complete disappearance of index lesion
- PR = at least 30% decrease in the longest diameter of the index lesion PD = more than 20% increase in the longest diameter of the index lesion SD = does not meet criteria for PR or PD
- Local tumor progression will be defined as >=20% increased size on CT scan compared to a CT scan from prior to treatment.
- Distant progression will be defined as any new tumor found outside of the pancreas or periampullary region on CT scan.

Pancreatic or periampullary tumor response will also be assessed by FDG-PET scans (when available) according to the following criteria:

- CR = target lesion becomes photopenic or standardized uptake value (SUV) ratio of tumor/liver less than or equal to 1
- PR = decrease in SUV ratio of tumor/liver (at least 30%) PD = increase in SUV ratio of tumor/liver (at least 20%)
- SD = no significant change in SUV ratio of tumor/liver

We will also determine PET response (in those patients who have undergone follow-up FDG PET scanning) with the new PERCIST criteria as reported by Wahl et al., defined as follows: (33)

- Complete metabolic response (CMR): complete resolution of 18F-FDG uptake within the measurable target lesions so that it is less than mean liver activity and indistinguishable from surrounding background blood-pool levels with no new 18F-FDG avid lesions
- Partial metabolic response (PMR): reduction by a minimum of 30% in the target lesion's 18F-FDG peak
- Stable metabolic disease (SMD): disease other than CMR, PMR, or progressive metabolic disease
- Progressive metabolic disease (PMD): 30% or greater increase in 18F-FDG peak in the target lesion or the development of new 18F-FDG avid lesions that are typical of cancer.

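### On the SUV-ratio PET scheme, complete response is a fixed level with no baseline condition, while the other categories are changes from baseline, so one lesion can fall into contradictory categories

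*Combined protocol and SAP*

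**What the plan says.** All references are to the combined protocol and SAP.

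Section 10.1 sets out several response schemes. On the tumor/liver SUV ratio, used when PET is available:

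- Complete response (CR): "CR = target lesion becomes photopenic or standardized uptake value (SUV) ratio of tumor/liver less than or equal to 1".
- Partial response (PR): a fall in the ratio of at least 30%.
- Progression (PD): a rise in the ratio of at least 20%.
- Stable disease (SD): "SD = no significant change in SUV ratio of tumor/liver", with no number attached.

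The same section gives a general comparison rule: "All subsequent scans (post-treatment) will be compared to the same pretreatment CT or PET/CT that was performed for radiation treatment planning". It also applies PERCIST in patients who have follow-up PET. There, complete metabolic response requires "complete resolution of 18F-FDG uptake within the measurable target lesions so that it is less than mean liver activity", uptake indistinguishable from blood-pool background, and no new avid lesions.

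PET is not mandatory. Section 7.1 says "Baseline FDG-PET/CT (dual phase) may be obtained for tumor staging and treatment planning purposes" and lets patients without it take part. A footnote to the Section 9 calendar says "FDG PET scan optional at baseline and at all follow-up intervals". Section 4 does not require an FDG-avid tumor. It does require chemotherapy before SBRT: "Please note that patients must have received at least two cycles of chemotherapy".

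**The concern.** Three of the four categories ask how far the ratio has moved. The ratio limb of CR asks only where it ended up. A lesion that was already at or below liver uptake before SBRT therefore meets the CR wording without any change, and some rising lesions meet it too. Because every patient has had chemotherapy and none has to have an avid tumor, a low ratio before SBRT is plausible.

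At stake is whether the PET categories can be interpreted. Section 10.1 says response will be assessed by PET when available. Section 10.3 sends all responses to independent radiology review at study completion, and Section 14 puts responses observed into the monthly summaries. Two readers following the text faithfully could file the same lesion under different categories.

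**Working it through.** The plan states no rate, power or sample size for PET response, so there is no figure of its own to reproduce. The check applies the written rules to pairs of ratios.

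**Rules (Section 10.1).** Let r0 be the baseline ratio, r1 the follow-up ratio, and change = (r1 − r0)/r0.

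- CR if r1 ≤ 1 (ratio limb)
- PR if change ≤ −30%
- PD if change ≥ +20%
- SD taken as anything between −30% and +20%. This range is an assumption, because the SD line has no number.

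**Literal application.**

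| r0 | r1 | Change | Categories met |
|---|---|---|---|
| 0.95 | 0.95 | 0% | CR and SD |
| 0.80 | 1.00 | +25% | CR and PD |
| 0.70 | 0.90 | +28.6% | CR and PD |
| 0.84 | 1.008 | +20% | PD only |
| 0.85 | 1.00 | +17.6% | CR and SD |
| 1.10 | 1.00 | −9.1% | CR and SD |
| 3.00 | 1.00 | −66.7% | CR and PR |

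**Where the conflicts lie.**

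- CR with no change needs r1 = r0 ≤ 1, so it covers any baseline ratio of 1 or less.
- CR together with PD needs 1.2 × r0 ≤ r1 ≤ 1, so r0 ≤ 1/1.2 = 0.833. Above that baseline, a 20% rise takes the ratio past 1 and only PD applies.
- With no baseline PET, change cannot be computed, so PR, PD and SD on the ratio cannot be assigned. The CR limb uses r1 alone and still can.

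**Effect of requiring r0 > 1 for CR.** Then r1 ≤ 1 < r0, so every CR involves a fall and cannot also be PD. CR still overlaps PR for large falls. It overlaps SD for small ones: at r1 = 1 the fall is under 30% whenever r0 < 1/0.7 = 1.43. An order of precedence is therefore needed as well.

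**Frequency, under assumptions only.** The documents give no SUV ratios. Suppose true baseline ratios are log-normal with median m and log SD s, each scan has independent log-normal error of SD 0.1, and SBRT has no effect. Then P(r1 ≤ 1) = Φ(−ln m / √(s² + 0.1²)).

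| m | s = 0.4 | s = 0.5 |
|---|---|---|
| 1.5 | Φ(−0.983) = 16% | Φ(−0.795) = 21% |
| 2.0 | Φ(−1.681) = 5% | Φ(−1.359) = 9% |
| 2.5 | Φ(−2.222) = 1% | Φ(−1.797) = 4% |
| 3.0 | Φ(−2.665) = 0.4% | Φ(−2.155) = 1.6% |

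Under the same assumptions, a lesion that is both CR and PD is rarer: about 1.0 to 1.4% at m = 1.5 and under 0.1% at m = 3.0. At m = 1.5 and s = 0.4, about 12.8 of 16.2 percentage points of CR come from lesions with a baseline ratio of 1 or less. A baseline condition would remove those and leave about 16.2 − 12.8 = 3.4 points from small falls across 1.

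**The case against.** The strongest reply is that nothing planned depends on this. PET response is not among the objectives or outcome measures in Section 3, and Section 11 names no analysis of it. Section 10.1 defines local and distant progression on CT, and the Section 10.2 time-to-event definitions use progression, metastasis or death. PET is optional throughout. All of this stands, and it confines the point to descriptive categories.

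A second reply is that the wording can be read more kindly. The verb of change in the CR line might govern both limbs, and the general comparison rule implies a reference scan. This stands only in part. Grammatically the verb attaches to the photopenic limb. The comparison rule sets no baseline level for CR, and it allows the reference scan to be a CT.

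A third reply is that PERCIST already supplies a stricter definition. It does, but the plan applies it in addition and does not say that it replaces or outranks the ratio scheme.

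A reader might also infer more than the text supports:

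- **That the flaw inflates a planned PET response rate and credits earlier chemotherapy to SBRT.** No such rate is specified, and the documents do not say how many tumors are at or below liver uptake before SBRT. Section 4.1 also admits patients whose recurrence was identified by radiographic progression or rising CA19-9, so quiet tumors at entry cannot be presumed common.
- **That any rising lesion can be both CR and PD.** This is limited to baseline ratios of 0.833 or less.
- **That the percentages above estimate the error in this trial.** They range from about 21% to under 1% depending on assumed inputs.

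**Conclusion.** The point holds as a defect in a stated rule. On the SUV-ratio scheme the CR level carries no baseline condition and no precedence, so the categories are not mutually exclusive. A lesion can be CR without changing if its baseline ratio is 1 or less, CR and PD together if its baseline is 0.833 or less, and CR with no baseline PET at all. These boundaries follow from the written thresholds. The overlap with SD also relies on reading an unchanged or slightly changed ratio as no significant change.

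The consequence is minor. It reaches only the descriptive SUV-ratio PET categories, and their frequency of misclassification is unknown. The primary acute toxicity estimate, CT-based progression, PFS, OS and the sample size of 38 are untouched.

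**What to change.** Add to the SUV-ratio criteria in Section 10.1, before the response review at study completion:

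1. CR can be assigned only to patients with a baseline PET and a baseline tumor/liver ratio above 1.
2. CR takes precedence over PR and SD.
3. Patients with a baseline ratio of 1 or less are not evaluable for CR but can still be classified as PD.
4. Patients with no baseline PET are not evaluable on this scheme.

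Item 3 matters because making such patients wholly non-evaluable would discard true progression, for example a rise from 0.9 to 3.0. A minimum 30% fall for CR is not needed to remove the CR/PD conflict. Imposing it on photopenic lesions would leave some in neither CR nor PR, for example a photopenic lesion falling from 1.2 to 0.9 (−25%). The price of omitting it is that a small fall across 1 still counts as CR, so the baseline ratio should be listed beside each PET CR.

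The cost is a few lines of text and no new scans. Recorded ratios can be reclassified. Somewhat fewer patients will be evaluable for PET CR, and the PET CR count may be lower.

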#### 10.2 Definitions

- Duration of Response: time elapsed between SBRT completion (i.e., the last day
  of treatment) and the first sign of local progression or the development of new
  metastatic disease.
- Progression-Free Survival: time elapsed from SBRT completion to documented local/regional or distant progression or death. Local PFS will be measured as the duration from SBRT to local progression or death from any cause.
- Overall Survival: Duration from SBRT completion to patient death.

# 10.3 Response Review

All responses will be reviewed independently by a board certified radiologist at the study's completion. Each image also will be reviewed by the PI with a concurrent review of the patient's medical records.

# 10.4 Criteria for Removal from Study

Patients will be removed from the study if consent is withdrawn or death occurs. The protocol director may also withdraw a patient from the study for one or more of the following reasons: failure of the patient to follow the instructions of the protocol study staff, the protocol director decides that continuing participation could be harmful to the patient, pregnancy (if applicable), the patient needs treatment not allowed in the study, the study is cancelled, other administrative reasons, or unanticipated circumstances. Patients who have been removed from or discontinue the study for administrative reasons will be followed for survival information until death.

# 11. STATISTICAL METHODS

#### 11.1 General Considerations

Statistical analysis of this study will be the responsibility of the Department of Biostatistics at Indiana University School of Medicine. Parameter estimates and relevant summary statistics will be reported for both efficacy and safety outcomes. Continuous variables will be summarized by means, medians, minima, maxima and standard deviations. Categorical variables will be summarized by frequencies and percentages. Missing data will not be imputed. Additional exploratory analysis will be conducted when appropriate. Changes from the analysis plan will not require an amendment to the protocol unless it changes a significant feature in the protocol. The statistical analysis methods are outlined below.

#### 11.2 Study Design

This is an open-label pilot study. No randomization or blinding is involved. Patients will be placed into dosing cohorts (A or B) depending on previous radiation therapy and followed for at least 1 year post-SBRT.

# 11.3 Criteria for Stopping Study

We expect the safety profile to be similar for Cohort A and B so will evaluate the stopping rule in the combined cohort. The expected Grade 4 or 5 treatment related AE rate from gemcitabine with SBRT is approximately 6% (Herman ref), and we would consider a 10% rate in our study to be unacceptable. An interim safety analysis is planned after every six patients are accrued and followed for 1 year to assess Grade 4 or 5 treatment-related AEs. If 3 or more out of 6, 4 or more out of 12, 5 or more out of 18, or 6 or more out of 24 patients have a Grade 4 or 5 treatment-related AE within one year, accrual will be terminated. These stopping boundaries represent where the lower bound of a 90% exact binomial confidence interval would be in excess of 10%.

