Using the linear-quadratic formulation, the biologically equivalent dose (BED) of the two proposed fractionation schedules are given in comparison to other commonly used schemes (table 1), including conventionally fractionated radiation, which is typically administered in 28 1.8-Gy fractions for a total dose of 50.4 Gy, usually with concurrent capecitabine-, 5-FU-, or gemcitabine-based chemotherapy. While the BED for the 5 Gy x 5 schedule (early/late 37.5/66.7) must necessarily be lower because it will be used in patients who have already been treated with radiation to the pancreatic region, that of the proposed 6.6 Gy x 5 schedule (BED early/late 54.8/105.6) closely approximates that of standard chemoradiation (BED early/late 60/83.3), but without concurrent chemotherapy and treating a smaller tumor margin (0.3 cm vs. ~2 cm). Furthermore, the proposed 6.6 Gy x 5 fractionation schedule has a much lower late BED (105.6 vs. 233.3) with a similar early BED (54.8 vs. 87.5) as the previous 25 Gy x 1 regimen. Finally, the use of five-fraction SBRT regimens may be able to spare circulating lymphocytes from radiation-induced toxicity that is mediated by high radiation doses to circulating blood. As radiation-induced lymphopenia has been linked to inferior overall survival in patients with both unresectable and resectable pancreatic cancers, it is logical to explore potential ways to decrease the risk and severity of this toxicity. (22, 23) Circulating blood dose is directly proportional to radiation field size and fraction number, suggesting that SBRT is a potentially promising strategy to reduce the risk of radiation induced lymphopenia, perhaps leading to improved outcomes, in patients with pancreatic cancer.

Table 1. Comparison of Radiation Fractionation Schemes in Pancreatic Cancer.							
RT Dose	Regional Nodes	Concurrent	Early BED	Late BED			
(Gy)	Treated?	chemo?	(Gy)	(Gy)			
/# Fractions			$(\alpha/\beta = 10)$	$(\alpha/\beta = 3)$			
50.4/28	Yes	Yes	60 Gy	83.3 Gy			
30/10	Yes	Yes	39	60			
25/5	No	No	37.5	66.7			
33/5	No	No	54.8	105.6			
25/1	No	No	87.5	233.3			

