# 11.5 Sample Size

It is anticipated that this study will last approximately 42 months (30 months of accrual and 12 months of additional follow-up while cohort matures). The total enrollment will be 38. With a 1 to 5 ratio of prior RT treatment to no prior RT treatment, we expect to enroll approximately 6 subjects in Cohort A and 30 in Cohort B. Six subjects in Cohort A will allow us to obtain only a preliminary sense of efficacy; however, we do not want to exclude this important cohort from the study since our focus is on safety. A sample size of 38 will allow us to estimate the primary outcome of acute (within 3 months of treatment) grade 3 or greater gastrointestinal and hematologic toxicity to within approximately 12% using a 90% exact confidence interval assuming the rate is similar to Herman et al. (28%).

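### The only numeric stopping rule pools both cohorts and gives the re-irradiated Cohort A little protection at the planned mix

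*Combined protocol and SAP*

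**What the plan says.** Section 11.3 sets one numeric stopping rule. Looks take place after every six patients have been accrued and followed for one year, and accrual ends if the number with a grade 4-5 treatment-related event reaches "3 or more out of 6, 4 or more out of 12, 5 or more out of 18, or 6 or more out of 24". The benchmark is an expected rate of about 6% from gemcitabine with SBRT, and the authors add that "we would consider a 10% rate in our study to be unacceptable". Each boundary is a count at which the lower limit of a 90% exact binomial interval is above 10%. The stated reason for pooling is an expectation: "We expect the safety profile to be similar for Cohort A and B so will evaluate the stopping rule in the combined cohort".

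Section 11.5 says "we expect to enroll approximately 6 subjects in Cohort A and 30 in Cohort B", a 1:5 ratio, within a total of 38. It explains why so small a group is kept: "we do not want to exclude this important cohort from the study since our focus is on safety". Section 11.2 assigns cohort by prior radiation alone. No section fixes the mix or order of entry.

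Elsewhere the protocol treats the cohorts differently. Section 2.2 says that the biologically equivalent dose for the Cohort A schedule "must necessarily be lower because it will be used in patients who have already been treated with radiation to the pancreatic region". Section 7.1.3 sets tighter normal-tissue limits for Cohort A. Section 2.3 supports re-irradiation with one series of 18 patients, with no grade 3 or greater toxicity reported at the Cohort A schedule.

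**The concern.** A pooled rule responds to the average of the two cohorts. With about one Cohort A patient for every five in Cohort B, a large excess in the re-irradiated group moves that average only a little. Cohort A is also the group for which the assumption of similar safety has the least direct support. The 6% benchmark comes from a trial that Section 2.2 describes as definitive five-fraction SBRT, not re-irradiation. If Cohort A's true rate were several times the 10% that the plan calls unacceptable, the rule would probably not stop accrual, although the plan keeps this cohort because its focus is on safety.

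**Working it through.** **Inputs.** From Section 11.3: boundaries 3/6, 4/12, 5/18, 6/24; criterion of a lower 90% exact limit above 10%; expected rate 6%. From Section 11.5: 1:5 ratio, about 6 A and 30 B, 30 months of accrual.

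**1. The plan's boundaries reproduce.** The lower limit for x events in n patients is the 5% quantile of Beta(x, n − x + 1).

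| n | boundary r | lower limit at r | lower limit at r − 1 |
|---|---|---|---|
| 6 | 3 | 15.3% | 6.3% |
| 12 | 4 | 12.3% | 7.2% |
| 18 | 5 | 11.6% | 8.0% |
| 24 | 6 | 11.5% | 8.6% |

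Each r is the smallest count that meets the criterion.

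**2. Cohort A's share at an exact 1:5 mix.** Cohort A supplies n/6 = 1, 2, 3, 4 patients against boundaries of 3, 4, 5, 6. The shortfall is two at every look, so at least two Cohort B events are needed even if every Cohort A patient has an event.

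**3. Probability of stopping at a fixed 1:5 mix.** This is an exact recursion over the four looks with 1 A and 5 B per block. As an example, take the first look with A at 100% and B at 6%. Stopping needs at least 2 events in 5 B patients: 1 − 0.94^5 − 5 × 0.06 × 0.94^4 = 1 − 0.734 − 0.234 = 3.2%. Over four looks this accumulates to 34%.

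**4. Probability of stopping in random order.** This is a simulation of at least 200,000 random orderings of 6 A and 30 B.

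| True rate in A (B at 6%) | Fixed 1:5 mix | Random order |
|---|---|---|
| 6% | 0.9% | about 1% |
| 30% | 4% | about 5% |
| 50% | 9% | about 12% |
| 100% | 34% | about 50% |

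Section 11.5's cohort sizes sum to 36, not 38. With 6 A and 32 B the random-order figures at 50% and 100% become about 11% and 45%. With no Cohort B events and A at 100%, the fixed mix never stops. In random order (6 A, 30 B) Cohort A alone reaches a boundary at some look in about 17% of orderings.

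**5. The same criterion applied to Cohort A alone.** The lower limits are 13.5% at 2/3, 9.8% at 2/4, 6.3% at 2/6 and 15.3% at 3/6. The boundaries are therefore 2 of the first 3, or 3 of the first 6. P(2 or more of 3) = 3p²(1 − p) + p³. The 3-of-6 boundary adds (1 − p)³ × p³ + 3p(1 − p)² × P(2 or more of 3).

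| True rate in A | 2 of 3 alone | 2 of 3 or 3 of 6 |
|---|---|---|
| 6% | 1.0% | 1.2% |
| 10% | 2.8% | 3.6% |
| 30% | 21.6% | 32.1% |
| 50% | 50.0% | 70.3% |

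**6. Timing if each look waits one year.** Assume even accrual and random order. The third Cohort A patient enters on average at position 3 × 37/7 = 15.9 of 36, which is month 15.9 × 30/36 = 13.2. One-year follow-up ends near month 25, when about 25.2/30 × 6 = 5 of the six are enrolled. For the 3-of-6 look to fall within accrual, the sixth Cohort A patient must enter by month 18, so all six must be among the first 21 patients. The chance is C(21,6)/C(36,6) = 54,264/1,947,792 = 2.8%. That look therefore falls after accrual in about 97% of orderings.

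**The case against.** A reader might infer from step 2 that Cohort A can never trigger the rule, whatever its event rate. The documents do not support that. The rule counts Cohort B events too, and the 1:5 ratio is an approximate expectation for the whole trial. If all six Cohort A patients entered among the first 24, their events alone could equal the 6/24 boundary. The impossibility holds only with the ratio exact at every look and fewer than two Cohort B events. What remains is a low probability of stopping.

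A reader might also infer that Cohort A is otherwise unmonitored. It is not. Section 14 requires continuous investigator review with monthly summaries to the DSMC. Sections 14.3 and 15.3.2 have SAEs reviewed monthly, and Section 14.2 allows early closure at any time. The study is open-label at one centre, so cohort membership is visible. These safeguards are real, but they are discretionary. None states a threshold or requires toxicity counts by cohort, and Sections 11.9 and 11.10 combine the cohorts for acute toxicity. The generic meeting form in Appendix III asks for discussion of dose levels, not for such a count.

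The lower prescription and tighter limits can fairly be read as the means of making safety similar, and the 18-patient series is favourable. The documents do not show that Cohort A is less safe. But if all 18 patients received the Cohort A schedule, 0 of 18 has an upper 90% exact limit of 1 − 0.05^(1/18) = 15.3%, so the series does not exclude the 10% rate called unacceptable.

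Finally, six patients support only a coarse boundary, and step 6 shows that a one-year wait would remove much of its value. Both points stand, and they shape the fix.

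**Conclusion.** The concern holds in this limited form: the pooled rule is weak for Cohort A, not incapable of responding to it. At a 50% true rate in Cohort A, five times the unacceptable level, with Cohort B at 6%, it fails to stop about seven times in eight in random order (12% stop) and about nine times in ten at a fixed mix (9%). The figures rest on 6 A and 30 B, Cohort B at the plan's 6%, independent events, and the four boundaries stated. The Cohort A rates of 30%, 50% and 100% are illustrations, not estimates. This is a cheap safety improvement. It does not undermine the primary estimate or show that pooling was unreasonable.

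**What to change.** Keep the combined rule and make two additions.

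- Tabulate the running grade 4-5 treatment-related count by cohort at each look and in the monthly DSMC summary.
- Add to Section 11.3: *The same criterion (lower 90% exact binomial limit above 10%) is also applied to Cohort A alone, that is, 2 or more of the first 3 or 3 or more of the first 6 patients. Events are counted as they occur, without waiting for one-year follow-up. If the criterion is met, accrual to Cohort A is terminated.*

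The cost is one short paragraph and one extra table line, with no added patients or procedures. The false-stop chance for Cohort A is about 1% at a 6% rate and about 4% at 10%.

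The benefit should be stated modestly. The 2-of-3 boundary is crossed with probability about 22% at a 30% rate and 50% at a 50% rate. The 32% and 70% figures include the 3-of-6 boundary, which under one-year follow-up would nearly always be assessed after accrual ends. Counting events as they occur recovers some of that, but how much depends on when events happen, which the documents do not give.

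If the sponsor keeps pooling only, Section 11.3 should say that the rule offers Cohort A little protection and that the cohort relies on DSMC judgement.
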